4.2.3. Rationale for the Selection of the Oral Corticosteroid Dosing Regimen

The oral prednisone starting dosage of 0.5 mg/kg/day (or equivalent OCS) and the subsequent dosage modification regimen (described in Section 6.8.1.3) are based on recommendations from European and Japanese guidelines^{25,26} Oral prednisone doses will be adjusted throughout the study for each participant based on their current BP disease activity to maintain CDA and to avoid relapse (Section 6.8.1.3).

4.2.4. Rationale for the Selection of Study Endpoints

4.2.4.1. Primary Endpoint

The primary endpoint was selected based on the BP disease status terminology described by Murrell et al. in 2012,²² in which the term CR off therapy is defined as "the absence of new or established lesions or pruritus while the patient is off all therapy for at least 2 months." Achieving a complete and stable absence of BP symptoms represents a clinically meaningful outcome and is expected to result in a significant improvement in patient quality of life.

Other than IMP, the only concurrent BP therapy permitted in ARGX-113-2009 is OCS; therefore, within the parameters of this study, "off OCS therapy" is considered equivalent to the AIBD expert definition of "off therapy."²²

In ARGX-113-2009, tapering of concurrent OCS therapy will be performed in a manner consistent with treatment guidelines, ^{24,25,26} while once-weekly dosing of IMP will be continued until the end of the 36-week treatment period. Tapering, and ultimately eliminating, concurrent OCS therapy reduces the risks of developing comorbidities associated with steroid therapy.

Avoiding such risks is particularly important for older adults (like those with BP), who historically develop serious comorbidities like osteoporosis, diabetes, and glaucoma following prolonged exposure to high doses of OCS. ^{27,28,29}

ARGX-113-2009 will assess whether participants have remained in CR while receiving efgartigimod PH20 SC or placebo and after having been off OCS for at least 8 weeks at the end of the 36-week treatment period. Achieving a sustained response to treatment is of particular importance to patients with BP, as the available evidence shows that many patients who achieve CR subsequently relapse within months. ^{30,31}

The selection of a 36-week treatment period is based on international guidelines for the treatment of BP, which recommend that systemic steroid doses should be tapered gradually so that minimal OCS therapy is achieved within 4 to 6 months after beginning treatment, and that OCS therapy may be subsequently stopped after the patient has sustained CR for 3 to 6 months. Therefore, a 36-week treatment period (approximately 9 months) is considered an appropriate duration to allow participants to achieve CR and stop concurrent OCS therapy.²⁴

4.2.4.2. Secondary Efficacy Endpoints

4.2.4.2.1. Key Secondary Endpoints (Part B Only)

Rationales for the selection of the key secondary efficacy endpoints for part B are summarized below. [Note: "Key" secondary endpoints are subject to hierarchical testing and alpha-control during part B only. During part A of the study, they will be assessed as standard secondary efficacy endpoints (without hierarchical testing/alpha-control).]

- 1. Cumulative dose of OCS from baseline to week 36: Currently, the standard of care for moderate-to-severe BP is OCS. Unfortunately, exposure to high doses of OCS results in an increased risk of developing serious comorbidities, especially in older adults. As a result, a goal in BP treatment is to reduce the patient's cumulative exposure to OCS. Therefore, this endpoint was selected to ascertain whether participants who are administered efgartigimod PH20 SC have lower cumulative OCS exposure values than participants who are administered placebo.
- 2. Proportion of participants who achieve an IGA-BP score of 0 while receiving efgartigimod PH20 SC or placebo and have been off OCS therapy for ≥8 weeks at week 36: This endpoint was selected because an IGA-BP score of 0 (defined in Section 4.2.2 and Section 10.6) represents a complete absence of BP skin lesions. As described in Section 4.2.4.1, the ability to remain free of clinical disease activity while limiting one's cumulative exposure to OCS for prolonged periods is particularly important for older adults with BP, who are more susceptible to serious comorbidities due to prolonged OCS exposure. 27,28,29
- 3. Proportion of participants who achieve CDA while receiving efgartigimod PH20 SC or placebo and remain free of relapse through week 36: This endpoint was selected because it is important to ascertain whether treatment with efgartigimod PH20 SC provides participants with BP prolonged and sustained relief from BP symptoms, and whether efgartigimod PH20 SC effectively prevents relapse.

- 4. Proportion of participants who are in CR while receiving efgartigimod PH20 SC or placebo and have been receiving minimal OCS therapy for ≥8 weeks at week 36: This endpoint was selected for the same reasons as those described for key secondary endpoint 3.
- 5. Changes from baseline in the 24-hour average itch score from the Itch NRS: As noted in Section 2.1, pruritus is among the signs/symptoms of BP; moreover, the itching that is associated with BP can be debilitating. This endpoint will determine if treatment with efgartigimod PH20 SC provides relief from pruritus, which is considered a clinically meaningful disease improvement.

4.2.4.2.2. Additional (or Other) Secondary Efficacy Endpoints (Parts A and B)

The additional secondary efficacy endpoints of this study (listed in Table 3 and Table 4) were selected to further characterize the efficacy of efgartigimod PH20 SC in participants with BP.

4.2.4.3. Safety Endpoints

The safety, tolerability, and health impact endpoints selected for this study are those considered to be standard for any clinical study evaluating the safety of an IMP.

4.2.4.4. Pharmacokinetics, Pharmacodynamics, and Immunogenicity Endpoints

The PK, PD, and immunogenicity endpoints selected for this study are those considered to be standard for any clinical study evaluating the manner in which an immunological IMP is processed by the body and how it targets the immune system.

4.2.5. Rationale for the Selection of Study Assessments

The BP disease assessment terminology and definitions applied in this study were adapted from those established by Murrell et al. in 2012.²² These terms and definitions are internationally accepted by AIBD medical experts and clinicians who treat patients with BP.

Disease severity and symptoms will be monitored throughout the study using the IGA-BP scale, the BPDAI, and the Itch NRS. The IGA-BP was developed in 2021 by medical experts in the field of AIBDs, and it is currently being used (along with the BPDAI) in other clinical studies of therapies for BP. The IGA-BP scale has specific guidance on equating the extent of skin lesions to disease severity (Section 10.6), while the BPDAI score also considers the presence of mucosal lesions (Section 10.7).² Pruritic symptoms will be measured using the Itch NRS (Section 10.8).^{32,33,34}

The BPDAI 2 and the Itch NRS 32,33,34 are validated and internationally accepted measures of BP disease severity and pruritus intensity, respectively.

The EQ-5D-5L,³⁵ DLQI,³⁶ and ABQoL³⁷ are validated and internationally accepted measures of patient QoL.

4.3. Justification for Selection of the Treatment Regimen and Dose

In ARGX-113-2009, study participants will either receive efgartigimod PH20 SC or placebo. At the time of this protocol's initial approval, efgartigimod PH20 SC had been safely administered to healthy participants and participants with gMG, primary ITP, CIDP, and pemphigus.

The SC route of administration offers convenience for participants with BP, their caregivers, and health care providers, because SC injections are easier to administer than IV injections. Additionally, the coformulation of efgartigimod with rHuPH20 permits SC dosing of higher volumes than typical SC injections, because rHuPH20 reduces resistance to fluid flow and increases dispersion and absorption of injected medicines and fluids, which allows for a larger volume to be injected with limited skin swelling or pain.

In BP, patients typically achieve CDA, PR, or CR only after receiving treatment for several weeks; sometimes even months of treatment are required before CR or PR is achieved. Moreover, patients with BP tend to relapse within a few months after achieving remission. Therefore, studies of BP must be of sufficient duration to assess the durability of efficacy of the IMP and the sustainability of remission while the patient is off OCS therapy. It is for these reasons that the sponsor has selected a 36-week treatment period for ARGX-113-2009.

Initially, the clinical development of efgartigimod was based on IV dosing. Results from phase 1 studies in healthy participants, phase 2/3 studies in participants with gMG, a phase 2 study in participants with ITP, and PK/PD modeling analysis showed that efgartigimod IV 10 mg/kg administered once weekly achieved nearly maximal reduction in serum IgG levels. Studies of participants with gMG and ITP also showed that efgartigimod IV 10 mg/kg administered once weekly resulted in clinical efficacy coupled with reductions in serum pathogenic autoantibody levels while maintaining a favorable safety/tolerability profile.

In ARGX-113-2009, participants will be administered efgartigimod PH20 SC as a fixed dose (rather than a dose that is adjusted weekly based on body mass), because this is more convenient for both the study participants and site staff. Results from a PK/PD modeling analysis indicated that efgartigimod PH20 SC 1000 mg administered once weekly would result in reductions in total IgG serum levels equivalent to a weekly dose of efgartigimod IV 10 mg/kg. Results from a phase 1 study comparing the PK and PD properties of IV and SC administration of efgartigimod in healthy participants (ARGX-113-1907) confirmed that 4 once-weekly injections of efgartigimod PH20 SC 1000 mg were noninferior to 4 once-weekly infusions of efgartigimod IV 10 mg/kg in reducing total IgG serum levels. Therefore, the sponsor has selected efgartigimod PH20 SC 1000 mg administered once weekly as the maintenance dose for ARGX-113-2009.

Still, given that IgG autoimmune activity is considered to cause the pathophysiology of BP, any therapy that targets this activity should be designed so that maximum reduction of total IgG serum levels occurs as rapidly as possible. Therefore, ARGX-113-2009 participants who are assigned to the efgartigimod PH20 SC arm will receive a dose of mg at baseline (week 0) and week 1. Initiation of treatment with 2 once-weekly doses of efgartigimod PH20 SC mg is predicted to achieve a nearly maximal reduction in total IgG serum levels within 2 weeks that is similar to that for once-weekly injections of efgartigimod PH20 SC 1000 mg at steady state.

4.4. End of Study Definition

The end-of-study definitions for ARGX-113-2009 are listed below:

- The end of part A of the study is defined as the date of the last visit of its last participant.
- The end of part B of the study is defined as the date of the last visit of its last participant.
- The end of the study is defined as the date of the last visit of the last participant in part B of the study. Alternatively, it is defined as the date of the last participant visit following the sponsor's decision to terminate the study for any reason.

A participant is considered to have completed the study under either of the following scenarios:

- The participant completes the EoTP visit at week 36 and chooses to immediately enroll in the OLE study ARGX-113-2010. The moment that a participant decides to roll over to the OLE study, they are considered to have completed ARGX-113-2009.
- The participant chooses not to enroll in the OLE study after completing the EoTP visit at week 36 and instead completes the 7-week treatment-free follow-up period (through week 43).

5. STUDY POPULATION

Prospective approvals of protocol deviations to recruitment and enrollment criteria, also known as protocol waivers or exemptions, are not permitted.

5.1. Inclusion Criteria

Participants can be included in the study only if all of the following criteria apply:

- 1. The participant is willing and able to do the following:
 - a. understand the requirements of the study
 - b. provide written informed consent (including consent for the use and disclosure of research-related health information)
 - c. comply with the study protocol procedures (including required study visits).
- 2B. The participant is male or female and has reached the local legal age of consent at the time of signing the informed consent form (ICF).
- 3. The participants have clinical signs of BP (ie, presence of bullae), with or without the presence of urticarial/eczematous/erythematous plaques or pruritus at the screening and baseline visits. The diagnosis of BP must be confirmed by positive histopathology and DIF before randomization to treatment assignment, and by positive serology (by IIF, CLEIA, or ELISA, according to local practice) at screening (Section 8.1.2).
- 4. The participant has an IGA-BP score of 3 or 4 at screening and baseline.
- 5. The participant has a Karnofsky performance status of at least 60% at screening.
- 6B. The participant agrees to use contraceptive measures consistent with local regulations and the following:
 - a. Male participants (contraceptive measures provided in Section 10.4.2.2)
 - b. WOCBP (defined in Section 10.4.1) must have a negative serum pregnancy test at screening and a negative urine pregnancy test at baseline before receiving IMP. (Section 10.4.2.1)

5.2. Exclusion Criteria

Participants are excluded from the study if any of the following criteria apply:

- 1. Other forms of pemphigoid (including but not limited to pemphigoid gestationis, drug-induced BP that resolves after culprit-drug withdrawal, anti-p200 pemphigoid, mucous membrane pemphigoid, and cicatricial pemphigoid), or other AIBDs (including but not limited to epidermolysis bullosa acquisita, pemphigus vulgaris, and exfoliative erythroderma)
- 2. Received unstable dose of treatments known to cause or exacerbate BP (eg, angiotensin converting enzyme inhibitors, penicillamine, furosemide, phenacetin, dipeptidyl peptidase 4 inhibitor) for at least 4 weeks prior the baseline visit
- 3B. Use of BP treatments other than OCS, such as TCS, conventional immunosuppressants (eg, azathioprine, cyclophosphamide, methotrexate, mycophenolate mofetil), or dapsone, including the following:

- a. sulfasalazine, IVIg, subcutaneous administration of immunoglobulin (SCIg), immunoadsorption or plasma exchange within 8 weeks of the baseline visit
- b. tetracyclines with or without nicotinamide at doses higher than the recommended daily allowance (RDA)/dietary reference intake (DRI) within 2 weeks of the baseline visit
- c. any monoclonal antibody (including rituximab or another anti-CD20 biologic) within 6 months of the baseline visit
- d. complementary therapies—such as traditional Chinese medicines, herbs, or procedures (eg, acupuncture)—within 4 weeks (or 5 half-lives) of the baseline visit, if the investigator determines that such therapies may interfere with the study's efficacy assessments and/or potentially risk the safety of the participant
- 4. Known contraindication to OCS therapy
- 5C.Clinically significant active infection that is not sufficiently resolved before baseline in the investigator's opinion
- 6A.Positive COVID-19 test result at screening (testing performed if required per local regulations)
- 7A. Any other known autoimmune disease or any medical condition that, in the opinion of the investigator, would interfere with an accurate assessment of clinical symptoms of BP, prevent participants from complying with protocol requirements, or put the participant at undue risk
- 8. History of malignancy unless deemed cured by adequate treatment with no evidence of recurrence for ≥3 years before the first administration of the IMP. Participants with the following cancers can be included at any time, provided they are adequately treated before their participation in the study:
 - a. Basal cell or squamous cell skin cancer
 - b. Carcinoma in situ of the cervix
 - c. Carcinoma in situ of the breast
 - d. Incidental histological finding of prostate cancer (tumor-node metastasis [TNM] stage T1a or T1b)
- 9. Clinical evidence of other significant serious diseases, have had a recent surgery, or who have any other condition that, in the opinion of the investigator, could confound the results of the study or put the patient at undue risk
- 10. Use of an investigational product within 3 months or 5 half-lives (whichever is longer) before the first dose of IMP
- 11. Previously participated in a clinical study with efgartigimod
- 12. Known hypersensitivity to any of the components of the administered treatments
- 13A. Positive serum test at screening for an active infection with any of the following conditions:
 - a. HBV that is indicative of an acute or chronic infection, unless associated with a negative hBsAg or negative HBV DNA test³⁸
 - b. HCV based on HCV antibody assay unless a negative RNA test is available

- c. HIV based on test results that are associated with an AIDS-defining condition or a CD4 count <200 cells/mm³
- d. HIV based on test results of a CD4 count ≥200 cells/mm³ not adequately treated with antiviral therapy
- 14A. Total IgG serum levels <4 g/L at screening.
- 15A. Current or history (ie, within 12 months of screening) of alcohol, drug, or medication abuse as assessed by the investigator
- 16A. Pregnant or lactating females and those who intend to become pregnant during the study
- 17. Live or live-attenuated vaccine received <4 weeks before baseline visit
- 18. Current participation in another interventional clinical study
- 19. Severe renal impairment (creatine clearance <30 mL/min/1.73 m²) at screening

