1.3. Schedule of Activities (SoA)

Table 1 presents the timing of visit activities to be performed throughout the entire study.

Table 1: Schedule of Activities (SoA)

Study period	Screening period ^a			Treatment period ^b Follow- up period ^c Other visits																			
Visit type	SCR	BL					Mai	ıdat	ory o	n-sit	e visit	:s ^d				Other weekly visits ^e	ЕоТР	F1	F2	ETDf	ESDg	UNSh	
Visit week		0	1	(D10)	2	3	4	8	12	16	20	24	26	28	32	_	36	39	43	ETD	ESD		
Visit day	-14 to -1	1	8	10	15	22	29	57	85	113	141	169	183	197	225		253						Applicable
Visit window (±days)	+7	_	±2	±1								±2						±	-3		-		protocol section
Informed consent	X																						Section 10.1.3
Inclusion/ exclusion criteria	X	X																					Section 5.1 Section 5.2
Randomization		X																					Section 6.3
Demography	X																						
Medical and surgical history	X																						Section 8.3.5
Histopathology/ DIF ⁱ	X																						
Karnofsky performance index score	X																						Section 10.5
QoL assessments		X							X				X				X			X	X		Section 8.2.2
Concomitant therapies/ procedures ^j	X	x	X	X	X	X	x	x	X	X	Х	X	X	X	х	х	X	x	х	X	X	(x)	Section 6.8
Height	X																						Section 8.3.2

Study period	Screening period ^a								Trea	ıtmen	ıt per	iod ^b						u	low- ip iod ^c	Ot	her vi	sits	
Visit type	SCR	BL					Mai	ıdat	ory o	n-sit	e visit	ts ^d				Other weekly visits ^e	ЕоТР	F1	F2	ETDf	ESDg	UNSh	
Visit week		0	1	(D10)	2	3	4	8	12	16	20	24	26	28	32	_	36	39	43	ETD	ESD		
Visit day	-14 to -1	1	8	10	15	22	29	57	85	113	141	169	183	197	225		253						Applicable
Visit window (±days)	+7	1	±2	±1								±2						+	₌3		-		protocol section
Weight	X	X	X		X	X	X	X	X	X	X	X	X	X	X	(x)k	X	X	X	X	X	(x)	Section 8.3.2
Physical examination and vital signs	X	X	X		X	X	X	X	X	X	X	X	X	X	X		X	X	x	X	X	(x)	Section 8.3.1 Section 8.3.3
ECG	X												X				Х			X	Х		Section 8.3.4
Urinalysis	X	X					X	X	X	X	X	X		X	X		X	X	X	X	X	(x)	Section 8.3.6.1
Active viral infection tests	X																						Section 8.3.7
COVID-19 test (performed if required per local regulations)	X																						Section 10.2.1.1
QuantiFERON-TB test	X																						Section 10.2.1.2
Serum pregnancy or serum FSH test ¹	X																						Section 8.3.8 Section 10.4.1
Urine pregnancy test for WOCBP (local laboratory)		x					X	x	x	X	X	X		X	Х		X	х	x	Х	X	(x)	Section 8.3.8
Clinical chemistry and hematology	X	X	X		X		X	X	X	X	X	X	X	X	X		X	X	X	X	X	(x)	Section 8.3.6.1

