8.3.7. Infections and Vaccinations

Patients with BP are susceptible to developing opportunistic infections. Concomitant and historical treatments by immunosuppressive or immunomodulatory therapies are comorbidity factors able to trigger or aggravate these infections.

In this study, some measures able to mitigate the occurrence of infections are required, and other precautionary measures optimizing the prevention of infections are recommended. For these reasons, the following actions are excluded for study entry:

- The administration of live or live-attenuated vaccines (eg, measles, mumps, rubella, rotavirus, smallpox, chickenpox, yellow fever) within the 4-week period before baseline visit or during the study (Section 6.8.2).
- Participants with a clinically significant active infection that is not sufficiently resolved before baseline in the investigator's opinion (exclusion criterion 5C).
- Participants who tested positive for an active viral infection at screening with HBV, HCV, and HIV (exclusion criterion 13A).
- Participants with total IgG serum levels <4 g/L at screening (exclusion criterion 14A).

The following measures are highly recommended before and during the study:

- To initiate or renew administration of non-live, inactivated, polysaccharide or recombinant vaccines (eg, tetanus, hepatitis A, hepatitis B, shingles) in participants susceptible to enter the study, at least 4 weeks before baseline visit.
- To vaccinate participants who are especially prone to or with an history of respiratory infections against Pneumococcus or Streptococcus pneumoniae.
- To vaccinate participants with seasonal vaccines (eg, influenza virus), especially those susceptible to enter the study in the winter months.
- To screen for possible infections (eg, respiratory, skin, mouth, eyes, nose and throat, genitals) and, if appropriate, initiate antibiotic treatment before baseline visit.
- To provide participants suffering from recurrent episodes of herpes simplex or herpes zoster with antiviral treatment throughout the treatment period of the study.

Any inactivated, subunit, polysaccharide, or conjugate vaccine will be allowed at the discretion of the investigator and if it is administered at least 48 hours predose or 48 hours postdose of the IMP.

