10.2. Appendix 2: Clinical Laboratory Tests

- The tests listed in Table 10 will be performed as described in the laboratory manual.
- Protocol-specific requirements for inclusion or exclusion of participants are detailed in Section 5.1 and Section 5.2.
- Additional tests may be performed at any time during the study as determined necessary by the investigator or required by local regulations.
- Investigators must document their review of each laboratory test report.
- Retesting during screening to assess eligibility may be performed at a local laboratory.

Table 10: Protocol-Required Laboratory Tests

Laboratory Test	Parameters		
Hematology	RBC count platelet count hemoglobin hematocrit	RBC indices: MCV MCH % reticulocytes	WBC count with differential: neutrophils eosinophils lymphocytes basophils monocytes
Clinical chemistry ^a	ALT AST ALP albumin ^b bilirubin (total and direct) BUN	calcium creatinine CRP GGT glucose glycosylated hemoglobin (HbA1c) potassium	sodium total protein ^b Lipid panel : total cholesterol HDL LDL (measured, not calculated) triglycerides
Routine urinalysis	Specific gravity pH, glucose, protein, blood, ketones, bilirubin, urobilinogen, nitrite, leukocyte esterase Microscopic examination (if blood or protein is abnormal)		
Pregnancy testing	Highly sensitive serum hCG pregnancy serum test at screening and urine test at other time points (as needed for women of childbearing potential, defined in Section 10.4.1) ^c		
Specialty laboratory tests	aPTT	INR	
Other screening tests	COVID-19 test (performed if required per local regulations) Tuberculosis QuantiFERON (or another regionally-approved IGRA test that has similar validity [eg, T-SPOT] ^d) Serology for HBV, HCV, HIV (exclusion criterion 13A and Section 8.3.7)		

ALP=alkaline phosphatase; ALT/SGPT=alanine aminotransferase/serum glutamic pyruvic transaminase; aPTT=activated partial thromboplastin time; AST/SGOT=aspartate aminotransferase/serum glutamic oxaloacetic transaminase; BUN=blood urea nitrogen; CRP=C-reactive protein; CT=computerized tomography; GGT=gammaglutamyl transferase; hCG=human chorionic gonadotropin; HBV=hepatitis type B; HCV=hepatitis type C; HDL=high-density lipoprotein; IEC=Independent Ethics Committee; IGRA=interferon gamma release assay;

INR=international normalized ratio; IRB=Institutional Review Board; LDL=low-density lipoprotein; MCH=mean corpuscular hemoglobin: MCV=mean corpuscular volume: RBC=red blood cell: WBC=white blood cell

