10.2.1.3. Hepatitis B Virus

Participants with an active acute or chronic hepatitis B viral infection at screening cannot be enrolled in the study.

The following combinations of serologic markers will be used to identify an active HBV infection (https://www.cdc.gov/hepatitis/HBV/PDFs/SerologicChartv8.pdf):

Table 11: Interpretation of Hepatitis B Serological Test Results

Test Result		lt	Interpretation	
HBsAg	Anti-HBc	Anti-HBs		
Positive	Positive	Negative	The patient cannot be enrolled in the study because the test results indicate an active HBV infection.	
Negative	Positive	Negative	The patient cannot be enrolled in the study because the test results indicate a low-level chronic HBV infection with impaired liver function. ^a	

anti-HBc=total hepatitis B core antibody; anti-HBs=hepatitis B surface antibody; HBsAg=hepatitis B surface antigen; HBV=hepatitis B virus

^aThis decision will be made by a medical doctor with sufficient experience in hepatology or infectious disease. Additional tests (eg, HBV viral load) may be required to determine the status of the participant.

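### Exclusion criterion 13A(a) lets a negative HBsAg alone lift the hepatitis B exclusion, bypassing the specialist decision that Table 11 sets for the HBsAg-negative, anti-HBc-positive, anti-HBs-negative pattern

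*Protocol*

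**What the plan says.** **Criterion 13A(a), Protocol 5.2.** A serum result indicating acute or chronic hepatitis B infection excludes the candidate, "unless associated with a negative hBsAg or negative HBV DNA test". Either negative result satisfies the exception.

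**Protocol 10.2.1.3.** The section opens with its own bar: "Participants with an active acute or chronic hepatitis B viral infection at screening cannot be enrolled in the study". Table 11 then lists the marker combinations used to identify active infection.

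- Row 1 (HBsAg positive, anti-HBc positive, anti-HBs negative): "The patient cannot be enrolled in the study because the test results indicate an active HBV infection". No footnote is attached.
- Row 2 (HBsAg negative, anti-HBc positive, anti-HBs negative): enrolment is barred because "the test results indicate a low-level chronic HBV infection with impaired liver function". Footnote a gives the decision to a doctor experienced in hepatology or infectious disease and adds: "Additional tests (eg, HBV viral load) may be required to determine the status of the participant".

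**Cross-references.** In the Schedule of Activities (Protocol 1.3), the row "Active viral infection tests" points to Section 8.3.7. Section 8.3.7 lists "Participants who tested positive for an active viral infection at screening with HBV, HCV, and HIV (exclusion criterion 13A)" among those who may not enter. Table 10 in Protocol 10.2 has the entry "Serology for HBV, HCV, HIV (exclusion criterion 13A and Section 8.3.7)". None of the three cites Table 11 or Section 10.2.1.3.

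**The concern.** Two current eligibility texts handle the same serology differently. One imposes a bar that only a specialist can lift. The other removes the exclusion on a result that every candidate with this pattern has by definition.

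What is at stake is participant safety. A candidate who is HBsAg negative but HBV-DNA positive would not trigger 13A(a). That candidate could go on to an IgG-lowering drug, for which Protocol 2.3.1 names serious infection as a risk. The drug is given with prednisone starting at 0.5 mg/kg/day, which Protocol 6.8.1.3 allows to rise to 0.75 or 1 mg/kg/day.

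There is also a conduct question. Protocol 5 and 8.1.1 allow no waivers. With two answers on eligibility, it is unclear whether a row 2 patient enrolled under 13A(a) without referral counts as a protocol deviation.

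**Working it through.** No arithmetic applies, and the plan gives no figure to reproduce. The check takes each rule as written and applies both to the same marker patterns.

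**Rule 1 (13A(a)).** The exclusion is lifted if HBsAg is negative OR HBV DNA is negative.

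**Rule 2 (Table 11).** Row 1 bars enrolment. Row 2 bars enrolment subject to the footnote a decision.

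| HBsAg | Anti-HBc | Anti-HBs | HBV DNA | 13A(a) read alone | Table 11 |
|---|---|---|---|---|---|
| − | + | − | + | Exclusion lifted | Row 2: barred, subject to specialist |
| − | + | − | − | Exclusion lifted | Row 2: barred, subject to specialist, who may clear |
| − | + | − | Not measured | Exclusion lifted | Row 2: barred, subject to specialist, who may ask for viral load |
| + | + | − | − | Exclusion lifted | Row 1: barred, no footnote |
| + | + | − | + | Excluded | Row 1: barred |

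Four things follow.

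1. In all three row 2 lines the negative HBsAg alone meets the exception in 13A(a). The DNA result plays no part, and neither a DNA test nor a referral is triggered.
2. With negative DNA, the two texts can reach the same outcome, because the specialist may clear the candidate. They differ in process. The line of safety concern is the first one, together with any unmeasured case that belongs there.
3. Row 1 has a separate mismatch. A negative DNA result lifts the exclusion under 13A(a), but row 1 bars the patient without qualification.
4. Hepatitis C shows no such divergence. Criterion 13A(b) and Table 12 both turn on a negative RNA test. The hepatitis B mismatch therefore looks like a drafting slip rather than a policy.

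**Where a site is led.** The Schedule of Activities leads to 8.3.7, and 8.3.7 leads to 13A. Table 10 leads to 13A and 8.3.7. Appendix 2 also says that eligibility requirements are set out in Sections 5.1 and 5.2. By contrast, the Schedule of Activities sends readers to 10.2.1.1 for COVID-19 and to 10.2.1.2 for tuberculosis, but not to 10.2.1.3 for hepatitis B.

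This compares protocol wording only. The external reference cited in 13A(a) was not available.

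**The case against.** The strongest reply is that the texts can be applied together. 13A(a) is an exception inside one exclusion criterion, and failing to trigger it makes nobody eligible. Section 10.2.1.3 has its own operative bar on active or chronic hepatitis B and says that the Table 11 patterns are used to identify it. A site that applies both texts refers the row 2 candidate. Table 11 sits in the same appendix as Table 10 and appears in the list of tables, so it can be found.

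Other safeguards exist. Criteria 5C, 7A and 9 let the investigator exclude. ALT, AST and bilirubin are measured at screening. The sponsor's designee and medical monitors review eligibility (10.1.7.3). Liver thresholds apply after dosing (7.1.2).

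Much of this stands, and it rules out three stronger readings that a reader might infer.

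- That the protocol as a whole permits enrolment of patients with active hepatitis B. It does not, because 10.2.1.3 bars them independently of 13A.
- That the two rules always give opposite outcomes. They do not, because row 2 with footnote a is a referral rather than an absolute bar.
- That the protocol already requires HBV DNA for row 2 patients. It does not, because footnote a leaves the test to the specialist.

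The reply does not remove the inconsistency. Footnote a says who decides a row 2 case, while 13A(a) read alone says that no decision is needed. The cross-references lead to 13A. None of the listed safeguards requires HBV DNA to be measured, and criteria 5C, 7A and 9 depend on the investigator's opinion.

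**Conclusion.** The point holds as a minor eligibility and safety inconsistency. Taken literally and alone, 13A(a) bypasses the specialist step for every row 2 candidate. Harm would require a site to follow 13A(a) and overlook 10.2.1.3, and the candidate to be HBV-DNA positive.

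Its size cannot be stated. The documents give no prevalence of row 2 serology, no DNA positivity rate within it and no number screened. The planned totals of about 40 and 120 participants are not the right denominator, because these patients arise among those screened.

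The estimand, alpha, power and sample size are unaffected. The textual mismatch is certain. How often it would matter in practice is not known.

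**What to change.** In the next protocol amendment:

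1. Amend 13A(a) so that a negative HBsAg does not lift the exclusion when anti-HBc is positive and anti-HBs is negative. Send that pattern to the specialist decision in Table 11 footnote a, with HBV DNA as the named test where the specialist needs it. Footnote a can then stay as it is.
2. Cite Table 11 and Section 10.2.1.3 from 13A(a), and add 10.2.1.3 to the viral-test row of the Schedule of Activities.
3. In the same edit, align Table 11 row 1 with the negative-DNA exception in 13A(a). The sponsor's medical team should decide which of the two texts stands.

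The cost is a few lines of wording. The downside is a possible short wait for a referral or a DNA result within the 2- to 3-week screening period, for this serology pattern only. No statistical section needs to change.
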